Cystometrics (Day -60 to -1) Cystometric testing (a bladder filling test during which patient sensations are recorded at various volumes and evidence of stress or urgency incontinence recorded) will be performed. Testing includes a urine pregnancy test and urine dipstick. See MOP Chapter "Study Procedures" regarding forms to be filled. If subject chooses to undergo an fMRI, they will have simulation of their fMRI task performed and may have urine and vaginal swab samples collected and stored for possible future analysis (For example, urine may be analyzed for biomarkers and microbiome analysis. See MOP Chapter "Study Procedures" regarding forms to be filled as noted in Section 5.1.

Baseline FMRI

FMRI (Day -60 to -1 for baseline and week 9 for follow-up) will be performed on women willing and able to have fMRI at baseline and follow-up. Testing includes a urine pregnancy test and urine dipstick. Forms to be completed include the fMRI procedure are noted in the "Study Procedures" MOP and has been described in the Protocol Section 5.1.

Other Baseline Tests/Questionnaires

Stanford Hypnotic Susceptibility Testing (Day -60 to week 1) this validated test may be administered by the hypnotherapist any time before the subject receives either their pharmacotherapy or hypnotherapy intervention. Its administration depends primarily on scheduling issues between the subject and hypnotherapist; attempts will be made to couple this testing with any of the subjects' pre-treatment visits (enrollment, cystometrics, fMRI) though the subject may have to come for a separate visit if this is not possible.

Patient Expectation Question (Day 0 and prior to treatment) the subject will be administered this question after randomization and prior to treatment. The question will be explained to the patient at enrollment, but will not be administered until the patient is notified regarding her group assignment by the Research Coordinator or her designee.

Randomization

Randomization to Treatment (Day 0) Subjects will be informed of their randomization to treatment by the Research Coordinator (or her designee if she is absent). Please refer to Statistics Section 9. Randomization will occur within 2-months of Enrollment. Treatment visits will be initiated within one month following randomization with a goal of initiating treatment within 1 week. However, subjects will be given the necessary time to prepare for their upcoming weekly treatment sessions.

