The principal purpose of this analysis will be to explore the mechanism of action of hypnotherapy when used to treat UUI, using pharmacotherapy as a control treatment that is not expected to exert its therapeutic effect via the brain. In addition we will explore the utilization of evoked activity and functional connectivity as biomarkers by correlating changes in these fMRI parameters with physiologic outcome measures, specifically UUI episodes. We understand that there is currently insufficient literature to determine the optimal method of assessing this correlation in the setting of a non-inferiority study design, and will look towards OCRA guidance on this aspect of the analytic plan in the future.

Treatment Assignment Procedures

Randomization to treatment

Study participants will be randomized to either pharmacotherapy or hypnotherapy groups using a computergenerated randomization scheme in varying permuted block sizes of 4-8. SAS 9.3[®] Proc-Plan software will create a randomization scheme of varying permuted block sizes of 4-8 to avoid severe inequality of group sizes for this 2 arm study. Subjects will be stratified based on fMRI performance and UUI severity (< 4 UUI episodes vs. \geq 4 UUI episodes on 3 day voiding diaries). UUI severity should be comparable in both groups because it is a potential risk factor for treatment failure. UUI severity will be defined by UUI frequency. Burgio⁸³ identified risk factors for unsuccessful behavioral treatment of UUI. Women with > 10 UUI episodes on baseline voiding diaries were much less likely to be completely continent after behavioral treatment. For purposes of this study, on a 3 day diary approximately 4 UUI episodes would be a potential risk factor for treatment failure and stratification will be performed in order to avoid UUI severity imbalances between the treatment groups. FMRI stratification will be performed to ensure appropriate representation of both treatment groups in the fMRI study.

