The UNMH CTSC biostatistics core will generate the computer randomization scheme for the study. [name] will generate the scheme before enrollment begins and will be blinded to subject allocation after the RCT is initiated; he will have no patient contact, research personnel will not disclose unique patient identifiers to him, and he will remain blinded to patient randomization until study completion. Trial randomization codes will be maintained by the CTSC and [name] (who is uninvolved with study analysis) will have the ability to break the blind. Breaking blinding is planned when all subjects in the RCT (N=152) have completed 12 month follow-up and when data collection and data quality checking have been completed. In the extremely unlikely event that the study is terminated or discontinued early due to excessive numbers of unanticipated and severe AEs determined to be warranted by the DSMB, the blind will be broken earlier than planned. The latter will occur after agreement by NCCAM and the DSMB, in which case the CTSC biostatistics office will be notified and the blind will be broken.

Group assignments will be placed in opaque, sealed envelopes by an individual otherwise unassociated with the study. The envelopes will be opened and subjects will be randomized only after subjects have signed informed consent and completed baseline evaluations. Investigators involved in interpreting fMRIs, investigators participating in the RCT, study personnel performing data entry and the study statistician will be blinded to knowledge of subjects' treatment groups. Investigator blinding will only be breached if a subject suffers an unexpected clinical event and investigator knowledge of the subject's treatment is essential to providing standard of care. Subjects cannot be blinded to treatment interventions as it will be obvious to them whether or not they are undergoing hypnotherapy or taking medications.

9.3 Definition of Populations (ITT versus Per Protocol) Intention to Treat:

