9.5 Outcomes

Outcomes documentation will not be reviewed and adjudicated by a committee. Outcomes will be analyzed by the Investigators and Study Statistician, [name], after the study is completed and the blind is broken using standard SAS® software on the Redcap® database maintained in a fashion consistent with UNM HRPO policy.

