9.6 Data Analyses

Specific Aim 1: Determine whether a mind/body therapy (hypnotherapy) is as, or is more effective and durable, in treating urgency urinary incontinence (UUI) than a non-mind/body treatment (pharmacotherapy)

Statistical Analysis: Improvement between hypnotherapy and controls will be compared at baseline and followup at 2, 6, 12 months. Because of the possibility that a number of subjects may be cured (i.e. report "0" urgency incontinence episodes) at follow-up on voiding diary, we will use a zero inflated Poisson (ZIP) generalized linear mixed model for the analysis and compare groups' urgency incontinence episodes. The ZIP model analysis is proposed because the data are expected to be relatively low counts with the potential of a large numbers of zeroes, particularly at 2 and 6 months, in excess of those allowed by the Poisson. Simple conversion to percent change will not correct the discrete nature of the data ("cures" become 100 percent change rather than 0 UUI count at 2 months), and standard least squares methods will not be appropriate. If there is no inflation at 0, i.e. standard Poisson regression is appropriate, then the associated log-linear model yields percent change as a natural parameter (by exponentiating the group effect). If there is significant inflation at 0, the confidence interval for percent change in the mean will be constructed by combining the two portions of the model with standard error estimated by the delta method, and checked via bootstrap methods. We will be able to derive mean UUI episodes as well as mean % change in UUI episodes following ZIP model analyses. All other parameters, which are normally distributed or continuous variables, will be compared using a linear mixed model analysis. It is unlikely that there will baseline differences between groups, given that this is a randomized controlled trial. If baseline differences between groups are found (e.g. incontinence duration, coexisting illnesses, prior treatment), appropriate variables will be added to the analysis as covariates. We will include pre-treatment patient expectations and hypnotic susceptibility as covariates in the analysis and determine if they are independent predictors of treatment response. We will not exclude subjects based on hypnotic susceptibility to increase the generalizability of our findings. We anticipate subjects' pre-treatment expectations will be an independent predictor of improvement in urgency incontinence & guestionnaire scores (the previously determined sample size is adequately powered to find a relatively small partial R² of .05¹³ between expectations and outcomes). The primary outcome measure will be change in UUI episodes from baseline to follow-up with a between group comparison, and not "cure". However, the term "cure" may be used for secondary analyses. As such, our definition of "cure" will be: absence of UUI episodes recorded on voiding diaries at 2, 6 and 12 month follow-up. Primary analyses will be performed using intention to treat. A per protocol analysis will also be performed; those who did not comply with the study interventions, extensively used other concomitant treatments known to improve UUI (e.g. used other UUI medications, underwent sacral neuro-modulation), or missed multiple treatment sessions will be considered to have been off protocol subjects. Similar analyses will be performed comparing group differences in change in questionnaire scores while accounting for covariates such as pain/interstitial cystitis (based on VAS pain scale and IC questionnaire) or bowel abnormalities (based on the CRADI-8), medical history and demographic variables (based on the medical history and demographic sheets) on the outcomes.

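### Aim 1: pre-treatment expectation, asked after the unblinded subject knows her arm, is listed as a covariate and is not kept out of the primary non-inferiority comparison

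*Combined protocol and SAP*

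**What the plan says.** **The test.** Section 9.2 declares non-inferiority if the lower one-sided 97.5% bound for the difference in mean percent reduction (hypnotherapy minus medication) exceeds -5. Section 9.3 makes intention to treat primary.

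**Named covariates.** Section 9.6 (Specific Aim 1) describes a zero-inflated Poisson (ZIP) mixed model and continues: "We will include pre-treatment patient expectations and hypnotic susceptibility as covariates in the analysis". The stated purpose is to see whether each predicts response in its own right. The section anticipates that "pre-treatment expectations will be an independent predictor of improvement in urgency incontinence" and cites a partial R² of .05.

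**Timing of those covariates.** Section 6.2.2 says the expectation question "will not be administered until the patient is notified regarding her group assignment". The schedule in 6.1 and Flow Diagram 1 also place it at or after randomization. Section 6.2.3 confirms that subjects are not blinded. Hypnotic susceptibility may be tested "any time before the subject receives either their pharmacotherapy or hypnotherapy intervention", with a window of Day -60 to week 1; randomization is Day 0.

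**Imbalance rule.** Section 9.6: "If baseline differences between groups are found (e.g. incontinence duration, coexisting illnesses, prior treatment), appropriate variables will be added to the analysis as covariates". No test, threshold or closed list follows. Section 9.5 places the analysis "after the study is completed and the blind is broken". Section 9.2 says "Breaking blinding is planned when all subjects in the RCT (N=152) have completed 12 month follow-up" and data checks are done; it describes no step that fixes the model first.

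**Strata.** Section 9.2: "Subjects will be stratified based on fMRI performance and UUI severity". Neither 9.3 nor 9.6 names a stratum as a model term.

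**The concern.** A covariate measured after an open-label assignment can itself be affected by that assignment. If the arms then differ in expectation, and expectation is related to outcome within arms, adjustment moves the arm contrast by the within-arm slope times the arm difference. Randomization gives no protection, because the difference arises after it. The adjusted contrast would no longer be the total effect of assignment that Section 9.3 makes primary. The decision rests on a single bound against a 5-point margin, so a shift of one or more points could change the conclusion, in a direction not known in advance.

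Two smaller matters concern the same model. The imbalance rule leaves the covariate set to be settled when group membership is known. The variables used to stratify randomization are not carried into the analysis.

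**Working it through.** **1. The plan's own figures.** Section 9.2 gives 52 per arm after 33% attrition: 152 × 0.67 / 2 = 50.9, close to 52. Its power statement cannot be reproduced directly because no SD is given. Solving SD = (5 + d) / (2.8016 × √(2/n)), with 2.8016 = z(.975) + z(.80):
- n = 52, d = 9: 14 / (2.8016 × 0.19612) = 25.48
- n = 60, d = 8: 13 / (2.8016 × 0.18257) = 25.42

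The two statements agree with each other. I use SD 25.45, so the unadjusted SE is 25.45 × 0.19612 = 4.99. I take one-sided alpha as 0.025; the same section also prints 0.25.

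**2. Expectation.** The slope at partial R² .05 is √.05 × 25.45 = 5.69 points per SD of expectation. The arm differences of 0.2 and 0.5 SD are my assumptions.
- Shift: 5.69 × 0.2 = 1.1 points; 5.69 × 0.5 = 2.8 points.
- Adjusted SE: 4.99 × √.95 = 4.865.
- If medication subjects expect more, one-sided error at a true -5 is 1 - Φ(1.96 - shift/4.865) = 4.2% and 8.5%.
- If hypnotherapy subjects expect more, power at a true +9 is Φ((14 - shift)/4.865 - 1.96) = 75% and 63%. Unadjusted, it is Φ(14/4.99 - 1.96) = 80%.

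Simulation (40,000 trials per case, total effect held fixed) gives error of 4.2% and 7.8% and power of 74% and 59%. It is a little lower because a covariate correlated with arm widens the SE: √(2/52) becomes about √(2/52 + d²/102), where d is here the arm difference in expectation in SD. With no arm difference, simulated error is 2.4% and power 81%, so there is no harm.

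A plain ZIP without random effects (assumed parameters, expectation R² about .045, 400 runs per case) gave shifts of about 1.2 points at 0.2 SD and 3.0 to 3.4 at 0.5 SD.

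**3. Imbalance rule.** Simulated at a true -5 with 3 or 5 assumed baseline variables:

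| Use of the rule | One-sided error |
|---|---|
| Applied mechanically | 1.1–2.4% |
| Most favourable model among qualifying variables, p<.05 cut-off | 2.5–2.9% |
| Same, standardized difference >0.2 | 3.1–4.0% |
| Most favourable of all subsets, 3 candidates | 4.0–4.7% |
| Most favourable of all subsets, 5 candidates | 5.7–9.2% |

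Each variable explains 2–10% of variance in rows 1–3 and 4–9% (correlation 0.2–0.3) in rows 4–5. The spread shows how far the answer depends on which models are assumed to be available.

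**4. Strata.** Power with strata in the model is Φ(14/(4.99 × √(1 - R²)) - 1.96). It rises by 0.4 points at R² .01 and 0.8 points at R² .02. At R² .05, leaving them out gives actual alpha of about 0.022 and power of 0.81 instead of 0.82.

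**The case against.** **The sentence may describe a predictor analysis.** Its stated purpose is to find predictors of response, and a power remark about a partial R² follows. Section 9.2 defines the test on population means without covariates. This reading is open. But the sentence stands in the Aim 1 model text with nothing to separate it from the primary comparison, whereas 9.6 does label its cure and per-protocol work as separate. What stands is that the plan must say which is meant.

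**The harm is hypothetical.** This stands as a limit on size. The documents give no arm difference in expectation, and .05 is a detectability figure rather than a predicted effect. If hypnotherapy subjects expect more, the test becomes conservative and loses power.

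**Expectation may be a true baseline item.** Section 10.1 lists it among the baseline questionnaires, and Section 3 says baseline questionnaires precede opening of the envelope. Section 6.2.2, which deals with its timing directly, puts it after assignment is known.

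**Susceptibility may always precede randomization.** The 6.1 schedule appears to mark only visits before randomization, but 6.2.2 allows later testing.

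**Stronger readings a reader might infer.** One is that the imbalance rule inflates type I error; applied mechanically it does not. Another is that omitting the strata invalidates the test; on the linear scale omission is conservative. The severity stratum is also a split of the baseline count, which 9.6 already uses in some form.

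**Conclusion.** The point holds as a conditional one. As written, 9.6 allows the primary contrast to be adjusted for a variable recorded after an unblinded subject knows her arm. If the arms differ in expectation by 0.2 or 0.5 SD, the estimate moves about 1.1 or 2.8 points against a margin of 5. Error at the margin is then about 4% or 8% in one direction; power at +9 is about 74–75% or 59–63% instead of about 80% in the other. These figures rest on the implied SD, a linear approximation, a slope set by partial R² .05 and assumed arm differences. The documents do not show that the result will be biased, nor in which direction.

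Susceptibility has the same weakness to a lesser degree. The imbalance rule is a matter of discretion with groups known, and its size cannot be fixed from the documents. The missing strata are a small, easily recovered loss. The plan should be changed, but nothing here shows the design to be unsound.

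**What to change.** Before the blind is broken, revise Section 9.6:

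1. State that the bound compared with -5 comes from one fixed primary model for the follow-up counts at 2, 6 and 12 months. Arm, time, arm-by-time and the baseline 3-day count (as a covariate) enter both the count and the zero parts; the severity and fMRI strata enter the count part.
2. Move both expectation and hypnotic susceptibility to a secondary predictor analysis. Moving both avoids a rule for mixed susceptibility test dates.
3. Replace the imbalance sentence with: no covariate is added to the primary model because of observed imbalance; any imbalance-adjusted model is a sensitivity analysis.

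The cost is wording, with no new data collection and no planned question lost. Section 11.2 says only that enrollment is complete; it does not show that all answers are in hand or that the blind is intact. If the blind has already been broken, report this model as post hoc alongside the planned analysis.

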Screening Visit: Study explained to patient. Pt. administered OAB Awareness Tool & given voiding diary instructions. Pt. given copy of consent and either has visit scheduled to sign consent or pt. given research coordinator's info. for future contact

Study Visit #1: Pt returns for study visit with her voiding diary and voiding diary reviewed for study eligibility/UUI frequency. Consent Signed. fMRI eligibility assessed. Past medical history & Demographics sheet & baseline questionnaires (OAB-qSF, ISI,PBBC, PISQ-12, IBS Module, CRADI-8, BPIC and vas pain questionnaire administered). POP-Q exam performed if not performed in last 12 months. Cystometrics scheduled. FMRI may be scheduled (for fMRI eligible & willing subjects) @ this visit or arrangements made to contact subjects regarding fMRI. Arrangements made to contact pts for scheduling future appts. and for patients to receive prophylactic antibiotics for catheterization(s). Behavioral Therapy reviewed & handouts given

Study Visit #2: Cystometry explained to subject. Urine pregnancy test and urine screen for UTI performed. Cystometry performed. FMRI patients will undergo fMRI task simulation and have urine and vaginal swab samples collected and stored for possible future analysis. Subjects may undergo hypnotic susceptibility testing at this time or any time prior to initiating study treatment.

Study Visit #3: FMRI (up to 80) Urine screen for UTI and pregnancy test performed. FMRI procedures again explained to subjects. FMRI performed. Subject incentives given or arrangements made to give incentives.

Patients Randomized (N=152). Patients notified of randomization and of pending appointment times and dates Pretreatment Expectation question administered

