within the last year (Pelvic Organ Prolapse Quantitation Exam, a validated examination recommended by the International Continence Society to standardize quantitation of patients' prolapse)

Arrangements will be made for cystometric testing, Stanford hypnotic susceptibility testing, and fMRI testing (if the subject is willing and without contraindications to fMRI). The expectation question will also be explained to subjects but will not be formally administered until the subject has been randomized to treatment. Adverse events will be tracked and followed up appropriately as noted in the DSMP. Subjects willing to participate in the fMRI study will be screened regarding whether or not they meet criteria for entry into the fMRI study. Subjects who meet criteria and who are willing to participate in the fMRI portion of the study will be scheduled for their fMRI or arrangements will be made to contact the subject to inform them of the date/time of their fMRI. The subjects will be randomized within a month of obtaining the consent.

Enrollment/Consent & Baseline Visit for Normative Controls ONLY participating in fMRI study (Day 0): In addition to the UUI study subjects described previously, a group of women without UUI and without OAB symptoms (also determined by the OAB Awareness Tool screening questionnaire) will be enrolled. This normative group (approximately 30-35 subjects) will keep voiding diaries, answer questionnaires, and undergo urine pregnancy and dipstick testing and cystometric testing followed by performance of an fMRI in order to compare baseline fMRIs in women with and without UUI. The consenting process will be the same as described for the UUI subjects. For this group of women, cystometrics may be performed the same day they are enrolled and fMRI will be scheduled for the following week (if this is not possible, the fMRI should be scheduled within 2 weeks). The procedures will be performed as outlined previously and subsequently in 6.4.3 and 6.4.4.

Baseline Cystometrics

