6.2.3 Blinding

This study is a single blinded trial. Every effort will be made to maintain masking until the study's completion of treatment of the 152 subjects in the RCT. Investigators involved in analyzing fMRIs, Co-Is, other than [name], participating in the RCT, study personnel performing data entry and the study statistician will be blinded to knowledge of subjects' treatment groups. Investigator blinding will only be breached if a subject suffers an unexpected clinical event and investigator knowledge of the subject's treatment is essential to providing standard of care. Subjects cannot be blinded to treatment interventions as it will be obvious to them whether or not they are undergoing hypnotherapy or taking medications.

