9.2 Sample Size and Randomization

Power Analysis/ Sample Size Calculation for Clinical RCT Specific Aim 1: We performed sample size calculations for change in UUI episodes and change in OABq-SF scores based on our pilot data & urgency incontinence literature.^{11,16,52} The study design will use a non-inferiority design to compare the primary outcome (change in UUI episodes in the hypnotherapy versus pharmacotherapy groups). With respect to the outcome variable of percent reduction in UUI episodes as determined by bladder diaries, we will use a one-sided noninferiority test at level alpha = 0.25 and a non-inferiority margin of 5%. If μ_h is the population mean percent reduction in incontinent episodes for the hypnotherapy group, and μ_m is the population mean percent reduction in incontinent episodes for the medications group, we will then test $H_0: \mu_h - \mu_m \le -5$ against the one-sided alternative $H_A: \mu_h - \mu_m > -5$ using significance level 0.025. If the null hypothesis is rejected then we may conclude hypotherapy is not inferior to medication therapy, on average, by more than 5%, and in fact may be superior to medication therapy, with respect to percent reduction in incontinent episodes. The test may be performed by computing the lower 97.5% one-sided confidence bound for $\mu_h - \mu_m$. If the lower confidence bound exceeds -5% we will conclude non-inferiority of hypnotherapy. Should that lower bound exceed zero we will conclude superiority. Assuming a subject drop-out, withdrawal and missing data rate as high as 33%, 52 subjects will be available for analysis in both hypnotherapy and medications groups. If $\mu_h - \mu_m \ge 9\%$, this sample size would provide power ≥ 80% for the non-inferiority test. Rigorous efforts will be made to reach an achieved attrition rate of 20-25%, such that approximately 60 subjects would be available for analysis in each group. This would allow for detecting non-inferiority if the actual $\mu_h - \mu_m \ge 8$ %. If the attrition rate at 1 year follow-up is < 20%, randomization of 152 subjects will allow us to detect even smaller inter-group differences than quoted previously.

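### Section 9.6 adjusts the Aim 1 arm comparison for a pre-treatment expectation score that is collected after women know their arm, and nothing keeps it out of the deciding non-inferiority model

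*Combined protocol and SAP*

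**What the plan says.** Section 9.6 (Specific Aim 1) describes a zero-inflated Poisson mixed model comparing the arms on urgency incontinence episodes, and states: "We will include pre-treatment patient expectations and hypnotic susceptibility as covariates in the analysis". The sentence goes on to say that the analysis will test whether these two variables predict response in their own right. The inclusion is unconditional, whereas the sentence before it adds other variables only when the arms are found to differ at baseline.

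The timing of the expectation question is set out in several places:

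- Section 6.2.2, Baseline Visit: it "will not be formally administered until the subject has been randomized to treatment".
- Section 6.2.2, Patient Expectation Question: "the subject will be administered this question after randomization and prior to treatment", and it "will not be administered until the patient is notified regarding her group assignment".
- Flow Diagram 1 (Section 3), in sequence: "Patients notified of randomization and of pending appointment times and dates Pretreatment Expectation question administered".
- Table 1 (Section 6.1) marks it in the Day 0 randomization column.

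Section 6.2.3 adds: "Subjects cannot be blinded to treatment interventions".

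Section 9.2 defines the deciding test on the difference in mean percent reduction, hypnotherapy minus medication, against −5: "The test may be performed by computing the lower 97.5% one-sided confidence bound for" that difference. It names no covariates. Section 9.3 makes the primary analysis intention-to-treat and gives no covariate list. Section 9.5 has outcomes analysed "after the study is completed and the blind is broken".

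**The concern.** A covariate in a randomized comparison should be one that assignment cannot affect. A woman who has just learned that she will have hypnotherapy, or tablets, may answer the expectation question differently because of that news. The score is then partly a result of assignment.

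Section 9.6 itself anticipates that expectation predicts improvement. If the arms also differ in expectation, adjusting for it removes the matching part of the arm difference. If other factors drive both expectation and outcome, the adjusted figure is not a clean direct effect either. In both cases the 5-point margin would be applied to a quantity other than the one Section 9.2 defines.

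The direction matters. Lower expectation on hypnotherapy pushes the adjusted difference up and makes a false non-inferiority claim more likely. Higher expectation pushes it down and costs power. Two statisticians following this plan could fit different primary models and reach different conclusions.

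**Working it through.** **Inputs from the plan (Section 9.2).** Margin 5 points; one-sided 0.025; 52 analysable women per arm with at least 80% power at a true +9; about 60 per arm at a true +8. The section also prints alpha as 0.25, but its stated significance level and the 97.5% bound agree with 0.025, which is used here.

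**The plan's own power figure.** No SD is given, so the 80% cannot be reproduced independently. Solving for the SD:

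- 52 per arm: (5 + 9) / [(1.960 + 0.842) × √(2/52)] = 25.5
- 60 per arm: (5 + 8) / [(1.960 + 0.842) × √(2/60)] = 25.4

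The two statements agree. With SD 25.45, power is 0.801 at 52 per arm and 0.799 at 60.

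**Assumed, not in the documents.** The arm difference in mean expectation, d (hypnotherapy minus medication, in SD units): 0, 0.2 or 0.5 in either direction. The R² between expectation and outcome: 0.01, 0.05 or 0.10. Section 9.6 gives 0.05 only as a size the trial could detect, not as an expected value.

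**Linear approximation.** Within-arm slope b = √R² × SD. The adjusted difference moves by −b × d. Its standard error is SD × √(1 − R²) × √(2/n) × √(1 + d²/4).

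At R² = 0.05:

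- b = √0.05 × 25.45 = 5.69 points per SD of expectation.
- A gap of 0.2 SD shifts the estimate by 5.69 × 0.2 = 1.1 points; a gap of 0.5 SD by 5.69 × 0.5 = 2.8 points.
- A shift equal to the whole margin needs 5 / 5.69 = 0.88 SD.
- With a 0.5 SD gap, SE = 25.45 × √0.95 × √(2/52) × √1.0625 = 5.01.
- Expectation 0.5 SD lower on hypnotherapy, true difference −5: type I error = 1 − Φ(1.960 − 2.845/5.01) = 8.2%.
- Expectation 0.5 SD higher on hypnotherapy, true difference +9: power = Φ((14 − 2.845)/5.01 − 1.960) = 60%.

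**Simulation of the adjusted linear model** (20,000 trials per cell, 52 per arm, total arm effect held at −5 or +9):

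| R² | Type I error, expectation lower on hypnotherapy by 0 / 0.2 / 0.5 SD | Power at +9, expectation higher by 0 / 0.2 / 0.5 SD |
|---|---|---|
| 0.01 | 2.6 / 3.0 / 4.4% | 80 / 76 / 69% |
| 0.05 | 2.6 / 4.2 / 8.2% | 81 / 74 / 59% |
| 0.10 | 2.5 / 5.1 / 12.5% | 83 / 73 / 52% |

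Without the covariate, type I error was 2.2–2.6% and power 79–80%.

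**Check closer to the planned model.** A zero-inflated Poisson model was run with about 4,000 trials per cell at one time point, without random effects. It assumed 7 episodes per 3 days at baseline, 30% remaining on drug and 20% structural zeros.

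- R² 0.05, expectation 0 / 0.2 / 0.5 SD lower: type I error 2.9 / 4.5 / 8.5% adjusted, against 3.3% unadjusted.
- R² 0.05, expectation 0 / 0.2 / 0.5 SD higher: power 87 / 81 / 70% adjusted, against 86% unadjusted.
- R² 0.01, expectation 0.5 SD lower: type I error 4.3% adjusted, against 2.4% unadjusted.

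Monte Carlo error on the type I figures near 3% is about √(0.03 × 0.97 / 4,000) = 0.3 points. The pattern matches the linear model.

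**The case against.** The strongest reply is that the text is ambiguous rather than wrong. The Section 9.6 sentence ends with a predictor question, the sentences after it concern prediction, and Section 9.2 writes the deciding bound with no covariates. An unadjusted deciding test plus a separate predictor model is a fair reading. It is not the only one. The covariate sentence is unconditional, stands in the paragraph that sets out the primary analysis, and is not labelled secondary. The ambiguity about the deciding model is what has to be removed.

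On timing, Section 10.1 lists the expectation question among baseline questionnaires, and Sections 3 and 9.2 place randomization after baseline questionnaires or evaluations. Those statements are general. Section 6.2.2 deals with this question specifically and puts it after notification.

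Harm needs an arm gap that the documents do not report, and only one direction inflates false non-inferiority. This stands, and it is why the figures are illustrations. The larger ones need the higher R² and the 0.5 SD gap together. Section 9.6 also says least squares does not suit these counts, and the zero-inflated check omits random effects and rests on assumed rates. The figures therefore show the size a bias could have, not what it will be.

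Section 9.5 says when outcomes are analysed, not when the model is chosen, so it is not a fault in itself. The gap is the missing covariate list for the primary model. The separate rule of adding covariates when the arms differ at baseline would also leave that list open to the data.

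**Conclusion.** The concern holds. Expectation is a planned covariate in the Aim 1 analysis, it is measured after women know their arm, and no text keeps it out of the model that decides non-inferiority.

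The bias is zero if expectation does not differ by arm. At R² 0.05 it is about 1.1 points for a 0.2 SD gap and 2.8 points for 0.5 SD, against a margin of 5. With the back-solved SD of about 25.5 and 52 per arm, the 0.5 SD case gives a type I error of about 8% or power of about 60%, depending on direction. At R² 0.01 and 0.2 SD the type I error is only 3.0%.

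The timing facts and the missing exclusion are certain; the actual size and direction are not known. Because the point concerns the deciding model, it must be settled before unblinded analysis.

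A minor related point, on which the verdict does not rest: Section 6.2.2 allows hypnotic susceptibility testing up to week 1, after assignment, although Table 1 marks only visits before randomization.

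**What to change.** Add to Section 9.6 that the primary 2-month non-inferiority model, and the main between-arm efficacy estimates, exclude the expectation score. Use that score only in an analysis labelled as exploratory (predictor or mediator) or as a sensitivity analysis. Leave hypnotic susceptibility out of the primary model unless it was tested before randomization in all women. Listing every covariate of the primary model in the same place would also settle the rule on baseline differences.

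Section 11.2 says enrolment is complete, so moving the question earlier is no longer possible. This is an analysis change only, to be recorded before the blind is broken.

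The cost is one or two sentences and the covariate's precision gain, about R² of the residual variance (1%, 5% or 10% at R² 0.01, 0.05 or 0.10). With R² 0.05 and no arm gap, linear-model power is 79% without the covariate and 81% with it. Sample size and data collection are unchanged, and the predictor question can still be answered.
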